7.5. Analysis of Secondary Endpoints - Diary Data

The User Population will be used for analysis of diary data. Descriptive statistics will be calculated by pooling data across sites. In addition, a supporting analysis will be performed using the Per Protocol Populations if more than 5% of participants in the User Population are excluded.

7.5.1 Definition of variables

Evaluable Cycle: A non-pregnant cycle (28-day equivalent) with complete bleeding diary data within the cycle.

Partial Evaluable Cycle: A non-pregnant cycle (28-day equivalent) with incomplete bleeding diary data within the cycle (e.g., only 10 of 28 days bleeding diary data are available within a cycle) either due to missing data or discontinuation.

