# 10.3.2 Daily Diary

For the first 12 months of use, participants will maintain a daily diary to record bleeding/spotting. Each form will collect one cycle of information consisting of 28 days of daily records. The form will also be used to record the use of any additional contraceptives (e.g. condoms) and coitus within that full 28-day cycle. Site staff will review responses carefully to ensure there are no questions about responses provided by the subject. The information from the daily diaries will be entered in the corresponding CRFs. Each site will retain originals of the completed diaries as source documents and certified copies will be uploaded to the study document repository or EDC at Health Decisions.

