# 19.2.2 Analysis of secondary endpoints

The standard 12-month continuation probability and its corresponding asymptotic 95% confidence interval for each study group will be estimated using the Kaplan-Meier method. In addition, a log-rank test will be used to compare early discontinuation rates between groups at the two-sided 0.05 significance level. Similar summaries and comparisons will also be made to assesses the probabilities of discontinuation by reason (e.g., IUD expulsion, failed IUD insertion, uterine perforation, pregnancy, personal/non-medical reasons, and other medically-related reasons), as well as self-reported desire to continue IUD use at the study exit but prior to unblinding the participant.

We will analyze bleeding diary data using the methods described by Mishell, et al. Statistics will include the mean, median, and range of the total number of heavy, moderate, light, or spotting days per 28-day cycle equivalent as defined on the daily diary (refer to Appendix 3). We will also report the per-subject mean and median number of cycles and the proportion of cycles that include any heavy bleeding, a prolonged bleeding episode (e.g., greater than 14 days), amenorrhea, or bleeding in more than 1/3 of days in the cycle. Details of the bleeding diary analysis will be included in the SAP, including procedures and definitions used to define individual cycles and to account for missing data.

In addition to diary data, summaries of bleeding and pelvic pain experienced between study visits (and reported on CRFs) will be described in contingency tables and displayed graphically in bar charts, by study visit and overall. Chi-squared tests for ordinal repose data (e.g., less than normal, normal, or more than normal pelvic pain) will be used to compare treatment groups at each visit. Evidence of informative censoring that is differential between groups will be explored using competing risk analysis; in the event such effects exist then analysis methods which account for informative censoring will be employed when comparing secondary outcomes between groups over time.

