7.5.2 Statistical methods

The descriptive statistics of per-subject mean and median number of evaluable cycles and the proportion of evaluable cycles that include any heavy bleeding, a prolonged bleeding episode (e.g., greater than 14 days), amenorrhea (absence of all bleeding and spotting), or bleeding in more than 1/3 of days in the evaluable cycle will be tabulated. In addition, descriptive statistics of bleeding diary data as described by Mishell, et al (2007) such as the mean, median, and range of the total number of heavy, moderate, light bleeding, or spotting days per evaluable cycle will be reported without considering the feature of repeated cycles from same study participants.

To incorporate the nature of repeated measures and partial evaluable cycles, a multinomial regression with generalized estimating equation (GEE) approach will be used to estimate and compare the mean, and total number of heavy, moderate, light bleeding, or spotting days per 28-day cycle equivalent between treatment groups (Liang and Zeger, 1986, and Lipsitz et al., 1994).

Note that if 1) there are sizeable participants discontinued early (e.g., 20% of IUD removal) due to increased menstrual blood loss or due to intermenstrual bleeding/spotting, and 2) the proportions of these two reasons of discontinuation are notably different between treatment groups (P-value < 0.1), the analyses of observed bleeding diary data are likely to be biased due to informative censoring and attrition (Hubacher et al., 2009). In this event, subgroup supporting analyses based on participants' discontinuation reasons related and non-related to blood loss/bleeding/spotting will be conducted. A stratified bleeding diary supporting analysis based on the same blood loss/bleeding/spotting related reasons will also be performed to compare the results from the above analyses. The findings of these supportive analyses will be interpreted cautiously.

For the analysis of pelvic pain data, the proportions of participants experiencing any pelvic pain during 28-day cycle, pelvic pain during period, outside of period, and both during and outside of period will be calculated using binomial distribution for each group, and compared between groups using chi-square tests. In addition, generalized linear models with GEE for repeated pelvic pain outcomes will be used to further explore the differences in frequencies of pelvic pain between study groups.

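### The bleeding tables for prolonged episodes, amenorrhea and bleeding on more than one third of days drop any 28-day diary form with a blank day, and no other analysis of these three measures uses such forms

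*SAP*

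**What the plan says.** Under Protocol 10.3.2 the diary is kept for the first 12 months: "Each form will collect one cycle of information consisting of 28 days of daily records".

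SAP 7.5.1 puts non-pregnant cycles into two classes. An evaluable cycle is "A non-pregnant cycle (28-day equivalent) with complete bleeding diary data within the cycle". A partial evaluable cycle is one with "incomplete bleeding diary data within the cycle (e.g., only 10 of 28 days bleeding diary data are available within a cycle"), whether the gap comes from missing data or from discontinuation. No tolerated number of blank days is given.

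SAP 7.5.2 then uses the classes differently:

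- It tabulates "the proportion of evaluable cycles that include any heavy bleeding, a prolonged bleeding episode (e.g., greater than 14 days), amenorrhea", and "bleeding in more than 1/3 of days in the evaluable cycle will be tabulated". The denominator is evaluable cycles only. The mean, median and range of heavy, moderate, light and spotting days are also reported per evaluable cycle.
- Partial cycles enter one analysis: "To incorporate the nature of repeated measures and partial evaluable cycles, a multinomial regression with generalized estimating equation (GEE) approach will be used". Its outcomes are numbers of heavy, moderate, light and spotting days.

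Protocol 19.2.2 describes the proportion of cycles with these features without limiting it to complete forms. It leaves the details to the SAP, "including procedures and definitions used to define individual cycles and to account for missing data".

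**The concern.** Vaginal bleeding pattern is a secondary objective, described by device. Three of its measures (a prolonged episode, amenorrhea, bleeding on more than 1/3 of days) rest entirely on forms with no blank day. One forgotten entry takes the other 27 recorded days out of these tables, and often the answer is already on the form:

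- A form with any recorded bleeding cannot be amenorrhea.
- A form with 10 recorded bleeding days already exceeds 28/3 = 9.33.
- A form with 15 consecutive recorded bleeding days is prolonged whatever happened on a blank day elsewhere.

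At stake are the precision of these tables and, if blanks are related to bleeding, their accuracy. For these measures the only missing-data procedure that the SAP gives is exclusion.

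**Working it through.** **Is there another route for incomplete forms?** The candidate sections are:

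| Place | What it does | Does it cover the three measures on incomplete forms? |
|---|---|---|
| SAP 6, missing data | Uses a participant's non-missing time points | No; it does not say how to classify a cycle with blank days |
| SAP 7.5, Per Protocol analysis | Changes the population | No; the cycle rule stays |
| SAP 7.5.2, multinomial GEE | Takes partial cycles | No; it models day counts by intensity |
| SAP 7.5.2, informative censoring | Subgroup and stratified analyses, conditional on bleeding-related discontinuation | No; the cycle rule stays |
| SAP section on last menstrual period and product satisfaction | Questionnaire on the last period | No; it asks about different measures |

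**Scale.** The plan states no figure for diary completeness, so there is nothing to reproduce. The 84.3% evaluable cycles in Protocol 19.1 concerns the pregnancy analysis and cannot be used here.

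The inputs are 28 days per form (Protocol 10.3.2) and an assumed daily blank probability q, independent between days.

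- Share complete = (1 − q)^28
- Share lost = 1 − (1 − q)^28
- Share with at most 3 blanks = sum over k = 0 to 3 of C(28,k) q^k (1 − q)^(28−k)

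| q per day | Complete | Lost | At most 2 blanks | At most 3 blanks |
|---|---|---|---|---|
| 0.1% | 97.2% | 2.8% | >99.9% | >99.9% |
| 0.5% | 86.9% | 13.1% | 99.96% | >99.9% |
| 1% | 75.5% | 24.5% | 99.7% | 99.98% |
| 2% | 56.8% | 43.2% | 98.2% | 99.8% |
| 3% | 42.6% | 57.4% | 94.9% | 99.1% |
| 5% | 23.8% | 76.2% | 83.7% | 95.1% |

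At q = 1%, exactly 1 blank has probability 21.3% and exactly 2 has 2.9%. Of the 24.5% of forms lost, (21.3 + 2.9)/24.5, about 99%, therefore have only one or two blanks.

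**Clustering.** Suppose blanks come only as whole missed weeks at the same 1% overall rate. The loss is then 1 − 0.99^4 = 3.9% of forms, and a 3-day tolerance recovers none of them.

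**Blanks related to bleeding (assumed).** Take a true 20% of cycles with prolonged bleeding, a daily blank rate of 2% in those cycles and 1% in the rest. The tabulated proportion is 0.20 × 0.568 / (0.20 × 0.568 + 0.80 × 0.755) = 0.1136/0.7174, or 15.8%.

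**The case against.** The strongest reply is that the comparison between devices does not depend on these tables. The GEE is the only diary-bleeding model named for comparing arms, and it takes partial cycles. The three measures are only tabulated. This stands, and it limits the weight of the point. A reader might infer that the SAP throws away incomplete diaries altogether, or that the device comparison is compromised; the text supports neither.

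A reader might also infer that the tables would describe only the most diligent diary keepers. That is not shown. With independent blanks at 3%, a woman with 13 forms has no complete form with probability 0.574^13, about 0.07%, so nearly every such woman still contributes. Blanks unrelated to bleeding cost precision and do not cause bias. The 15.8% figure above needs an assumption that the documents neither support nor exclude.

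The size is assumed throughout, and there are safeguards. Staff review the responses (Protocol 10.3.2). Diaries are gone over with the participant at Visits 2 to 5 to correct errors (Protocol 12.1). Dates are prefilled, and there is an explicit box for no bleeding (Protocol Appendix 3). These may keep blanks rare. Their reach is limited in the second half of the year: seven forms go out at month 6 and come back at month 12, and the month-9 call only reminds the participant to fill them in (Protocol Tables 04 and 05).

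Requiring complete data is also defensible for amenorrhea and for a run of more than 14 days, because a blank day can change the classification. Scaling counts to 28 days cannot score either one. Any tolerance therefore needs an explicit rule for blanks.

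**Conclusion.** The point holds as a cheap improvement to a descriptive secondary analysis. On the plain reading of complete against incomplete, a single blank day removes a form from the SAP 7.5.2 tabulations. For prolonged bleeding, amenorrhea and the over-1/3 measure, nothing else in the plan uses that form.

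The loss is anywhere from negligible (2.8% of forms at 0.1% blanks per day) to large (43% at 2%). These figures rest on an assumed rate and on independence between days; clustered blanks would lose fewer forms.

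It would be tempting to add that a tolerance repairs the loss of forms cut short by removal. It does not: only a record that stops on day 25, 26 or 27 would pass a 3-day limit, and the SAP's own example of 10 of 28 days stays excluded. The case rests on sporadic blanks.

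**What to change.** In SAP 7.5.1 and 7.5.2, for these tabulations only:

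1. Also accept forms with at most 3 unrecorded days. The number 3 is a judgement, since the documents supply none. With independent blanks, limits of 2 and 3 differ little up to about 2% blanks per day.
2. For the over-1/3 measure, use recorded days as the denominator. The cutoff stays at 10 bleeding days with 27 or 28 recorded days (27/3 = 9, 28/3 = 9.33) and becomes 9 with 25 or 26 (25/3 = 8.33, 26/3 = 8.67).
3. For runs and amenorrhea, score a blank as bleeding if the recorded days on both sides are bleeding days, and as no bleeding otherwise. Show the result again with blanks scored the opposite way.
4. Keep the complete-form tables as a sensitivity analysis.
5. Report by arm the number of forms excluded, separating sporadic blanks from forms cut short by removal.

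The cost is SAP wording and minor programming, with no new data collection. The downside is that a few tolerated forms may be misclassified for amenorrhea, for a run of more than 14 days or near the one-third cutoff. The opposite-scoring and complete-form tables would show whether that matters.

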7.5.2 Statistical methods

The descriptive statistics of per-subject mean and median number of evaluable cycles and the proportion of evaluable cycles that include any heavy bleeding, a prolonged bleeding episode (e.g., greater than 14 days), amenorrhea (absence of all bleeding and spotting), or bleeding in more than 1/3 of days in the evaluable cycle will be tabulated. In addition, descriptive statistics of bleeding diary data as described by Mishell, et al (2007) such as the mean, median, and range of the total number of heavy, moderate, light bleeding, or spotting days per evaluable cycle will be reported without considering the feature of repeated cycles from same study participants.

To incorporate the nature of repeated measures and partial evaluable cycles, a multinomial regression with generalized estimating equation (GEE) approach will be used to estimate and compare the mean, and total number of heavy, moderate, light bleeding, or spotting days per 28-day cycle equivalent between treatment groups (Liang and Zeger, 1986, and Lipsitz et al., 1994).

Note that if 1) there are sizeable participants discontinued early (e.g., 20% of IUD removal) due to increased menstrual blood loss or due to intermenstrual bleeding/spotting, and 2) the proportions of these two reasons of discontinuation are notably different between treatment groups (P-value < 0.1), the analyses of observed bleeding diary data are likely to be biased due to informative censoring and attrition (Hubacher et al., 2009). In this event, subgroup supporting analyses based on participants' discontinuation reasons related and non-related to blood loss/bleeding/spotting will be conducted. A stratified bleeding diary supporting analysis based on the same blood loss/bleeding/spotting related reasons will also be performed to compare the results from the above analyses. The findings of these supportive analyses will be interpreted cautiously.

For the analysis of pelvic pain data, the proportions of participants experiencing any pelvic pain during 28-day cycle, pelvic pain during period, outside of period, and both during and outside of period will be calculated using binomial distribution for each group, and compared between groups using chi-square tests. In addition, generalized linear models with GEE for repeated pelvic pain outcomes will be used to further explore the differences in frequencies of pelvic pain between study groups.

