#### 7.2 Inclusion Criteria

- 16-40 years
  - o 16 and 17 year olds, where permissible by state regulations and local Institutional Review Board (IRB) approval
- Sexually active, anticipating at least one act of vaginal intercourse per menstrual cycle with a male partner and at risk for pregnancy
- seeking contraception, and willing to use the study IUD as the only contraception method
- willing to be randomized to one of the two copper IUDs
- has an intact uterus and at least one ovary
- has a history of regular menstrual cycles; defined as occurring every 21-35 days when not using hormones, and with a variation of typical cycle length of no more than 5 days
- able and willing to provide written informed consent
- agrees to follow all study requirements
- not currently pregnant or at risk for luteal phase pregnancy based on history of unprotected intercourse

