# 26 APPENDIX 3: DAILY DIARY

Note: The diary includes bleeding definitions to ensure consistent assessment of bleeding amongst study subjects. However, the definitions are based upon the use of tampons or pads. Subjects using menstrual cups should be instructed to use their best judgment to assess their level of bleeding each day since the bleeding definitions within the diary will not apply.

CCN016 IUD Daily Diary	Start Date of 28 Day		Version 01.00 2017 0509
Subject Number:	interval:	MMM-DD-YYYY	

B	Date	MMM-DD	MMM-DD	MMM-DD	MMM-DD	MMM-DD	MMM-DD	MMM-DD	MMM-DD	MMM-DD	MMM-DD	MMM-DD	MMM-DD	MMM-DD	MMM-DD
ı	None				0	-				-				0	
e e	Spotting			0	-	0			-	-		0	0	-	
d	Light bleeding			0									0		
i	Moderate bleeding		п												
n	Heavy bleeding	 			0			0	-			0		0	
g	Diary Day	1	2	3	4	5	6	7	8	9	10	11	12	13	14

В	Date	MMM-DD													
ī	None			D						0		10	D		
e e	Spotting		-	-						-			-	-	
d	Light bleeding	0		0						0	0	0	0	0	
i	Moderate bleeding	0	0	0	0	-		0	0	0		0	0	0	-
n	Heavy bleeding			В	_			0		0		0	В	_	
g	Diary Day	15	16	17	18	19	20	21	22	23	24	25	26	27	28

	No	Yes
Did you have vaginal intercourse in this 28 day interval?		
60 - 86	No	Yes
Did you use any other contraceptive method in this 28 day interval?		
	Condom	Other
If any other contraceptive method was used, what method was used?		

Dates will be prepopulated for you by the study staff.

Complete bleeding information every day between your study visits. Provide responses on intercourse, contraceptive method and pain experienced for each full interval prior to finishing each diary form. Remember to bring the completed diary form back to your next visit. If you have any questions on how to complete the form, please ask the clinic staff.

Did you have any pelvic pain during this 28 day interval?	No	Yes					
If yes, was this pain during your period, outside of your period, or both during and outside your period, or both during and outside your period.	period?		During period	Outside of	period	Both during and of period	outside

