7.3.1 Definition of variables

Pregnancy: The endpoint of the primary objective is incident pregnancy. The following data will be examined to determine whether a pregnancy has occurred:

- Positive pregnancy test result recorded on the Pregnancy Test, Pregnancy Notification, or Pregnancy Outcomes forms;
- Pregnancy otherwise reported on Adverse Event, IUD Removal or End of Trial forms.

Estimated Date of Conception (EDC): The Investigator will estimate the date of conception based upon results of transvaginal ultrasound examination, quantitative β -hCG determination, last menstrual period (per daily diary information), pelvic and/or abdominal examination, and pregnancy outcome.

Without looking at the treatment group assignment in the LiveTrial eCRF, the Medical Monitors will review the assigned date of conception and other relevant data to confirm the date of conception to be used for analysis. If the Medical Monitors assign a different date during this adjudication process, their reason for assigning a different date will be documented.

On-treatment Pregnancy: An on-treatment pregnancy is a pregnancy in which the EDC is 1) on or after the date of IUD insertion and 2) on or before 7 days of post IUD removal. In addition, a "worse case" scenario will be used that considers pregnancies as "on-treatment" if the EDC or date of expulsion is not known.

Study Cycle (28-day equivalent): Every 28 study days with information about whether the participant used other contraceptive methods within those 28 study days will be considered as a study cycle (e.g., study day 28 will be considered the end of cycle 1, and day 56 for the end of cycle 2, etc., so long as information on use of other methods is documented for those periods). Note: cycles where conception occurred or where a participant had the IUD removed will be considered 'study cycles' (even if the EDC or removal did not occur on the 28th day), so long as there is information on other contraceptive methods use up until the time of conception defined as an on-treatment pregnancy or IUD removal.

Study Cycles (described previously) with no diary data will be excluded from the pregnancy analysis. Two types of pregnancy analysis cycle will be used for the efficacy analysis:

Primary Pregnancy Analysis Cycle: A primary pregnancy analysis cycle is a study cycle that

- 1. contains an on-treatment pregnancy, or
- 2. has both these characteristics:
 - a. reported sexual intercourse in the cycle and

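### SAP 7.5.2 counts prolonged bleeding and amenorrhea per fixed 28-day diary form: it has no rule for episodes that cross a form edge, and its amenorrhea definition can label some forms from women with regular long cycles

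*SAP*

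**What the plan says.** Bleeding pattern is a secondary objective in both documents. The diary runs for the first 12 months. Under Protocol 10.3.2, "Each form will collect one cycle of information consisting of 28 days of daily records", and the form in Protocol Appendix 3 tells the woman "Dates will be prepopulated for you by the study staff". Nothing ties the start of a form to the start of a period.

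SAP 7.5.1 makes this block the unit of analysis. An evaluable cycle is "A non-pregnant cycle (28-day equivalent) with complete bleeding diary data within the cycle". For the pregnancy analysis, SAP 7.3.1 counts its blocks from study day: "study day 28 will be considered the end of cycle 1, and day 56 for the end of cycle 2".

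SAP 7.5.2 then tabulates, among other things, the proportion of evaluable cycles that include "a prolonged bleeding episode (e.g., greater than 14 days), amenorrhea (absence of all bleeding and spotting"), and the proportion with bleeding on more than one third of days. Protocol 19.2.2 lists the same per-cycle measures and leaves the definition of individual cycles and the missing-data rules to the SAP. The SAP defines the evaluable unit. It does not define a bleeding episode, does not say which unit an episode belongs to if it spans two forms, and does not say whether spotting days count toward an episode.

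Protocol 7.2 requires regular menses, "defined as occurring every 21-35 days when not using hormones".

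**The concern.** A block of 28 calendar days is a sound unit for counting bleeding days. It is a poor unit for two features that depend on consecutive days.

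A prolonged episode can begin in one form and end in the next. If each form is judged alone, the run is split and may not exceed 14 days on either side. Conversely, the gap between two normal periods in a long regular cycle can be 28 days or more. A form that falls wholly inside that gap has no bleeding or spotting and meets the stated amenorrhea definition, although the woman is menstruating regularly and within the eligible range.

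At stake is how the two devices are described on a named secondary endpoint. Prolonged bleeding could be under-reported, and amenorrhea could be reported in women who do not have it. Two programmers working from the present text could also produce different tables.

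**Working it through.** The documents give no figure for this point, so there is none to reproduce. The check enumerates positions exactly.

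**Inputs from the documents:** form length 28 days (Protocol 10.3.2, SAP 7.5.1); prolonged means more than 14 days, so at least 15 (SAP 7.5.2); more than one third of days means more than 28/3 = 9.33, so at least 10 (SAP 7.5.2); eligible cycle length 21 to 35 days (Protocol 7.2).

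**Assumptions:** a run is equally likely to start on any of the 28 form days; each run is judged within the form; every run day counts as bleeding; each woman's cycle length C and number of bleeding or spotting days b are constant. The documents do not give b for either device, so it is shown as a range.

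**Prolonged bleeding.** Split a run of L days (15 to 28) into a days in the first form and L − a in the next. The run is missed when both parts are at most 14, that is, when a lies between L − 14 and 14. That gives 14 − (L − 14) + 1 = 29 − L of the 28 start days, so the missed share is (29 − L)/28. From 29 days on it is zero. The run also escapes the one-third row when both parts are at most 9, that is, when a lies between L − 9 and 9, which gives 19 − L start days (zero from 19 days on).

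| Run length | Missed by the >14-day row | Missed by both rows |
|---|---|---|
| 15 days | 14/28 = 50.0% | 4/28 = 14.3% |
| 16 days | 13/28 = 46.4% | 3/28 = 10.7% |
| 17 days | 12/28 = 42.9% | 2/28 = 7.1% |
| 20 days | 9/28 = 32.1% | 0 |
| 28 days | 1/28 = 3.6% | 0 |

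**Amenorrhea.** The bleed-free gap is C − b days. A 28-day form fits inside it only if C is at least 28 + b, and then in C − b − 27 of the C possible phases. The share of forms affected is max(0, C − b − 27)/C.

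| Cycle length C | b | Share of forms labelled amenorrhea |
|---|---|---|
| 32 or less | 5 | 0 |
| 33 | 5 | 1/33 = 3.0% |
| 34 | 5 | 2/34 = 5.9% |
| 35 | 4 | 4/35 = 11.4% |
| 35 | 5 | 3/35 = 8.6% |
| 35 | 7 | 1/35 = 2.9% |
| 35 | 8 or more | 0 |

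The affected forms cluster by woman. Over 13 consecutive forms (365/28 is about 13) with C = 35 and b = 5, 15 of the 35 possible starting phases (43%) give two or three such forms, and the other 20 give none.

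**After the change.** If runs are built on the joined daily record, the missed share for 15- to 28-day runs falls from (29 − L)/28 to zero wherever the adjacent forms are complete. If amenorrhea required a bleed-free interval longer than 35 days, no regular cycle of 35 days or less could meet it, because its gap is C − b, which is below 35.

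**The case against.** The strongest objection is that the SAP never says a run is cut at the form edge. It speaks of cycles that include a prolonged episode, and an episode overlapping the cycle would also fit. The diary is dated and kept daily, so runs can be rebuilt. This stands: for prolonged bleeding the defect is a missing rule, not a stated wrong one. Judging within the form remains the natural reading, because the form is the unit, completeness is assessed within it, and no linking rule is given.

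Several further points stand. The one-third row catches most split runs, though it also counts scattered days and so cannot itself report prolonged episodes. SAP 7.5.2 attaches no test to these rows; the planned diary comparison is the GEE (generalized estimating equations) analysis of day counts, which form edges do not affect. Uniform start days are an assumption: under Protocol 11.1.2, same-day insertion in women not using hormones falls in the first 7 days of the cycle, so phases may not be uniform. Protocol 21.3.1 expects about half of ParaGard users to have more flow and more bleeding days, and about 20% to have intermenstrual spotting or bleeding. Either would lower the amenorrhea share.

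A reader might infer more: that half of all prolonged bleeding is lost, that regular long cycles in general are scored as amenorrhea, or that the comparison between devices is biased. The documents support none of these. The 50% applies only to runs of exactly 15 days. The amenorrhea label needs a cycle of at least 28 + b days and then touches a minority of forms. The same rule applies to both arms, and the documents give no run lengths by device from which to derive a bias. A reader might also conclude that 84-day reference periods are required. That would depart from the 28-day unit in Protocol 19.2.2, and an incomplete form could then cost a whole period; it is a trade-off, not a necessity.

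**Conclusion.** The point holds as a gap in definitions with a measurable effect on two descriptive rows.

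- **Prolonged bleeding.** The SAP lacks a rule for episodes that cross a form edge. If they are judged within the form, the loss is largest for runs just over the threshold, falls steadily with run length and is gone from 29 days. The one-third row removes much of the practical harm, and all of it by 20 days.
- **Amenorrhea.** Here the rule is stated, and followed as written it labels some forms from regularly menstruating eligible women. This happens only toward the long end of the eligible cycle range and depends on the assumed number of bleeding and spotting days.

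Both results rest on uniform phase and constant patterns within a woman. The primary pregnancy analysis and the GEE comparison of bleeding days are not touched. The case for acting is that the endpoint is a named one, the labels would otherwise mislead, and the correction needs no new data.

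**What to change.** In SAP 7.5.1 and 7.5.2:

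1. Join each woman's adjacent dated forms into one continuous day record.
2. Define a bleeding episode on that record, and state whether spotting days count.
3. Count each prolonged episode once, in the form in which it starts.
4. Either relabel the amenorrhea row as *28-day interval without bleeding or spotting*, or score amenorrhea on the continuous record as a bleed-free interval longer than the 35-day eligible maximum.
5. Keep the 28-day form as the unit for counts of heavy, moderate, light and spotting days.

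The cost is SAP wording and a little programming. One rule has to be added: how to censor an episode that adjoins an incomplete form, or one still running when the diary stops, since its full length is then unknown.
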